Statistical Analysis Plan for Protocol

“Cathelicidin and Vitamin D: Impact on Populations At-Risk and with COPD” (NCT02464059)

Version 27 April 2020

This document serves as an addendum to the approved protocols related to NCT02464059 [“Cathelicidin and Vitamin D: Impact on Populations At-Risk with COPD” (Protocol version 1.2; 9/6/17; IRB 16-2200) and “Cathelicidin and Vitamin D: Impact on Populations with COPD (Protocol 8/23/17; IRB 17-2170)” to outline the detailed statistical analysis plan for the prespecified outcomes of this study. In the event that information in this document is discrepant from the original protocols (as it relates to endpoints or analyses), this detailed statistical analysis plan supersedes the original protocols.

Analysis populations

Full analysis set (FAS): All screened patients with informed consent and at least baseline bronchoscopy.

Descriptive Summary of Study Cohort

Using the FAS, the following variables will be summarized using descriptive statistics (mean and standard deviation, min, max, median) and graphical displays (boxplots, histograms) as appropriate.

- Demographics and clinical variables
- Baseline pre- and post-bronchodilator spirometry measurements

Specific pre-defined outcomes are defined below along with the planned analytical approach.

1.1. Primary Outcomes

1.1.1. Change from Baseline in Lung Cathelicidin Level at 8 Weeks [Time Frame: Baseline and 8 weeks]

- Change from baseline to 8 weeks in bronchoscopic lavage lung cathelicidin levels after vitamin D supplementation (comparison between pre- and post-supplementation cathelicidin levels using paired t-tests for repeated measures)

2.1. Secondary Outcomes

2.1.1. Change from Baseline in Blood Cathelicidin at 8 Weeks [Time Frame: Baseline and 8 weeks]

- Change from baseline to 8 weeks in blood cathelicidin levels after vitamin D supplementation (comparison between pre- and post-supplementation cathelicidin levels using paired t-tests for repeated measures)

Analysis plan

Paired sample (dependent) t-test to evaluate for differences in BAL cathelicidin (primary outcome) and plasma cathelicidin (secondary outcome) between pre- to post-vitamin D supplementation. Specifically, we will compare mean cathelicidin levels (log transformed as needed for normality) from pre- and post-supplementation BAL samples, and separately from plasma samples. P-values and 95% confidence intervals will be calculated for all estimates.

All tests with p value < 0.05 will be interpreted nominally as statistically significant. There will be no imputation for missing data.

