PROTOCOL

Cathelicidin and Vitamin D: Impact on Populations At-Risk and with COPD

ClinicalTrials.Gov Registration NCT02464059

UNC PROTOCOL

Version 1.2

Updated September 6 2017

SECTION 1. Study Overview

SECTION 2. Recruitment

SECTION 3. Detailed study visit procedures

SECTION 4. Reporting events

SECTION 5. Study visit checklists

SECTION 6. Study forms

SECTION 7. Laboratory procedures

SECTION 8. Bronchoscopy procedures

SECTION 1: Vitamin D Study Overview

1.1: Introduction and Background: Understanding mechanisms leading to decrements in lung function, the physiologic hallmark of obstructive lung diseases including chronic obstructive pulmonary disease (COPD), are necessary to inform interventions to improve lung health. The antimicrobial peptide cathelicidin, and its primary regulator vitamin D, has been implicated in the development and progression of chronic lung disease. Cathelicidin has bactericidal and inflammatory activities in the lung and is regulated by vitamin D levels.

1.2: Purpose of the Study: The purpose of the study is to determine the effect of vitamin D replacement on blood and lung cathelicidin levels in populations at-risk or with established COPD. The antimicrobial peptide cathelicidin, and its primary regulator vitamin D, has been implicated in the development and progression of chronic lung disease. We hypothesize that oral vitamin D supplementation will raise cathelicidin levels in the pulmonary compartment, thereby potentially restoring relative lung cathelicidin deficiency. To test this hypothesis, we will recruit from two sites: 1) Johns Hopkins (via the Subpopulations and Intermediate Outcome Measures in COPD Study (SPIROMICS) study of individuals with established COPD (NA_00035701: PI [name]) and 2) UNC COPD Clinic for individuals at-risk for COPD (smokers with preserved lung function). This MOP reflects procedures for the UNC site.

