At each site, we will measure blood and lung lavage cathelicidin levels in 20 vitamin D insufficient individuals (10 participants with serum 25-OH Vitamin D<10 ng/ml and 10 participants with serum 25-OH vitamin D between 10-20) before and after eight weeks of oral vitamin D supplementation to determine the effect of vitamin D supplementation on cathelicidin levels. Completion of this project directly or indirectly works towards ultimately understanding if a readily measurable blood marker, cathelicidin, can inform who may benefit from vitamin D supplementation to prevent chronic lung disease. The results from this application would lead to a therapeutic intervention study that will provide further opportunities to improve our understanding of the relationship between vitamin D, cathelicidin and lung function.

1.3 Objectives:

To evaluate the effect of oral vitamin D supplementation on plasma and lung cathelicidin measures in individuals with vitamin D insufficiency. Our primary analysis will include comparison between pre- and post-supplementation cathelicidin levels using paired t-tests for repeated measures

The study procedures outlined in this proposal specifically do not include any assessment of outcomes related to disease treatment, mitigation, cure, or prevention. We do not assess change in lung function over time, symptom scores, exacerbation risk, sputum production, pneumonia outcomes or any other assessment related to treatment/mitigation of COPD. The only outcome collected is BAL and blood samples to measure cathelicidin pre- and post-vitamin D supplementation (along with standard safety outcomes that are not related to any disease process). The lack of any assessment of outcomes related to diagnosis, cure, mitigation, treatment or prevention of disease demonstrates that such outcomes are not the scope of the proposed study.

1.4 Overall Project Design:

The design of the study to complete this aim will be in the format of a baseline and repeat bronchoscopy after oral supplementation with 50,000 IU vitamin D3 weekly for eight weeks in individuals with reduced vitamin D levels. The specific study data collection is outlined in the table below.

- Participants will undergo a screening assessment (visit S0) to determine the presence of vitamin D insufficiency (serum 25OH-VitD <20 ng/ml) as well as normal renal function and calcium levels. Pre- and post-bronchodilator spirometry will be performed to document normal lung function.

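### The SAP does not say whether the at-risk and COPD populations are pooled, plans no estimate for either one, and leaves the scale of the effect estimate to the data.

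*SAP*

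**What the plan says.** The SAP title is "Cathelicidin and Vitamin D: Impact on Populations At-Risk and with COPD", and section 1.2 of the UNC protocol gives the purpose as to "determine the effect of vitamin D replacement on blood and lung cathelicidin levels in populations at-risk or with established COPD". The same section sets the size: "At each site, we will measure blood and lung lavage cathelicidin levels in 20 vitamin D insufficient individuals". The SPIROMICS/Bayview protocol, section 2.2, also sets a goal of 20.

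The two groups cannot overlap. Section 2.4 of the UNC protocol requires post-bronchodilator FEV1/FVC of at least 0.70 and current smoking. Section 2.4 of the SPIROMICS/Bayview protocol requires FEV1/FVC below 0.70 and admits current or former smokers.

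The SAP has one analysis set: "Full analysis set (FAS): All screened patients with informed consent and at least baseline bronchoscopy". It has one primary outcome (1.1.1): "Change from baseline to 8 weeks in bronchoscopic lavage lung cathelicidin levels after vitamin D supplementation". Its Analysis plan names a paired t-test for lavage and another for plasma, with no term for population, protocol or site. On scale it says only "we will compare mean cathelicidin levels (log transformed as needed for normality) from pre- and post-supplementation BAL samples". On reporting it says "P-values and 95% confidence intervals will be calculated for all estimates", and every p-value below 0.05 is to be read nominally as significant. On missing data: "There will be no imputation for missing data".

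Section 1.3 of each protocol carries its own sentence naming paired t-tests as the primary analysis. The SAP overrides the protocols only where they disagree with it.

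**The concern.** Two things are left open.

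**Which patients the primary test covers.** The single analysis set and single primary outcome point towards one test on about 40 pairs. The separate primary-analysis sentences and separate targets of 20 point towards one test per protocol. No sentence settles it. If the test is pooled, a study titled for two populations has no planned figure for either, and where responses differ the pooled mean describes neither.

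**Which quantity is estimated.** On the raw scale a paired t-test estimates a mean difference. On the log scale it estimates a ratio of geometric means. The SAP gives no rule for choosing, does not say whether normality is judged on the levels or on the paired differences, and names no back-transformed summary. A reader cannot know in advance what the promised confidence interval will be an interval for.

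**Working it through.** The plan states no power, effect size, SD or loss rate, so there is no figure of its own to reproduce. From the documents: 20 per population, a paired t-test, and a 0.05 level (two-sided assumed). The SDs, correlation, distributions and loss below are assumptions.

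**1. Pooled interval against each population's own change.** Take normal changes with within-population SD 1 and 20 + 20 pairs. Suppose the populations change by 0.66 and 0 SD; 0.66 is the change that 20 pairs detect with 80% power.
- Pooled mean = (0.66 + 0)/2 = 0.33.
- SD of the 40 changes = sqrt[(38 × 1 + 40 × 0.33²)/39] = 1.04.
- Noncentrality = 0.33 × sqrt(40)/1.04 = 2.00, against a critical t(39) of 2.02, so power is about 49%.
- CI half-width ≈ 2.02 × 1.04/sqrt(40) = 0.33. Each population's true change lies 0.33 from the pooled mean, so coverage is about half.

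Simulation (200,000 trials per row) gives:

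| True changes (SD) | Pooled power | Pooled CI covers a population's own change |
|---|---|---|
| 0.66 and 0 | 49% | 51% |
| 0.5 and 0.2 | 57% | 85% |
| 0.5 and 0.3 | 69% | 91% |
| 0.4 and 0.4 | 69% | 95% |

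With 16 + 16 pairs (assuming 20% have no second bronchoscopy), the first row becomes 40% and 60%. A per-population interval covers its own mean in 95% of trials throughout.

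**2. Precision per population.** Half-width = t(0.975, n−1)/sqrt(n):
- n = 20: 0.47 SD
- n = 16: 0.53 SD
- n = 40 (pooled): 0.32 SD

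As a ratio with log-change SD 0.7 or 1.0, that is times or divided by 1.39 or 1.60 at n = 20, against 1.25 or 1.38 pooled. A difference between populations (20 v 20) has half-width 0.64 SD and needs about 0.91 SD for 80% power, so a test between them is not worth planning.

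**3. The two scales answer different questions.** For lognormal levels, arithmetic mean ratio = geometric mean ratio × exp[(s_post² − s_pre²)/2].
- Geometric ratio 1, log SD 0.7 to 0.8: exp(0.15/2) = 1.08.
- Geometric ratio 1, log SD 0.7 to 1.0: exp(0.51/2) = 1.29.
- Geometric ratio 1.25, log SD 1.0 to 0.7: 1.25 × exp(−0.51/2) = 0.97, the opposite direction.

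**4. The unstated rule.** With lognormal pairs, correlation 0.5 and log SD 0.3 to 1.0, Shapiro-Wilk on levels and Shapiro-Wilk on differences chose different scales in 32–58% of trials at n = 20 and 8–60% at n = 40.

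Power at a ratio of 1.5, log SD 0.7 / 1.0:

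| | Always log | Check on levels | Check on differences |
|---|---|---|---|
| n = 40 | 94.8 / 70.3% | 94.8 / 70.3% | 93.2 / 69.2% |
| n = 20 | 69.4 / 41.1% | 69.5 / 41.2% | 64.0 / 38.3% |

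The largest losses are 94.8 − 93.2 = 1.6 points at n = 40 and 69.4 − 64.0 = 5.4 at n = 20. Type I error is 4.9–5.2% with either check. Reporting whichever scale gives the smaller p would give 6.3–7.1%.

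**The case against.** **The SAP may not pool at all.** It is an addendum to two protocols, each with its own paired t-test and its own target of 20, and it contradicts neither. A reader might infer from the single analysis set that pooling is planned and the per-population estimates are absent by design. The documents do not support stating that as fact. Nor can the COPD side be checked fully: the SAP cites a protocol of 8/23/17, while the one available is version 1.7 of April 2016. This objection stands, and the point is framed as silence on pooling.

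**The harm is not general.** Coverage near one half belongs to the most extreme case modelled; at 0.5 and 0.3 SD the interval misses in 9%. Nothing in the documents suggests the populations respond differently, and a pooled interval is not built to cover a subgroup mean. This also stands. What remains is that the study's stated question concerns two populations and the SAP plans a figure for neither.

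**The scale wording is ordinary practice.** A reader might infer that choosing the scale from the data inflates false positives. Under a formal check it does not, and the power cost is small. The gap lies in what is estimated, and the divergence in step 3 appears only if the variance changes.

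**No imputation might be read as dropping values below the assay limit.** No passage mentions an assay limit, so this is not part of the point.

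**Adding estimates adds tests.** As the SAP is worded, each new estimate would get a p-value read as significant below 0.05. With no effect, the chance that at least one of two is significant is 1 − 0.95² = 9.8%, or about 12% with the pooled test included (simulation). This is right, and the fix must deal with it.

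**Conclusion.** The point holds in limited form. The SAP does not state whether the at-risk and COPD populations are pooled, and it plans no estimate by population although title and purpose name both. If pooling is meant, the cost depends on how far responses differ: coverage of a population's own change runs from 95% (equal) through 91% and 85% to 51% (0.66 against 0 SD), assuming 20 + 20 complete pairs and equal SDs.

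The conditional log transformation leaves the effect measure undefined until the data are seen. That is a matter of interpretation, not of error rate: there is no type I inflation under a formal check, and at most about 1.5 points of power are lost at n = 40 and roughly 3 to 5 at n = 20, for lognormal levels with correlation 0.5.

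Both parts deserve a change to the SAP. Neither invalidates the design. Confidence is medium, because the cited COPD protocol was not available and every SD is assumed.

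**What to change.** Amend the SAP's Analysis plan, before the cathelicidin values are seen if that is still possible:

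1. State whether the primary test is one pooled test or one test per protocol. Only the study team knows which was meant. If it is per protocol, say how the two results form the primary conclusion; 20 pairs give 80% power at 0.66 SD, against 0.45 SD for 40.
2. Fix the outcome as log(post/pre) for lavage and for plasma, reported as a geometric mean ratio with 95% CI.
3. If pooled, include a population term centred at its sample mean. The estimate is unchanged. Power rises from 49% to 53% at 0.66 and 0 SD, and about 0.1 point is lost if the changes are equal.
4. Report the ratio and 95% CI for each population as estimation only, with no test between populations.
5. Amend the sentence that promises p-values for all estimates, so that no p-value or significance statement attaches to the per-population results.

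Cost: SAP wording and a few lines of code, with no change to enrolment, visits or the primary 5% level. There are two downsides. Per-population intervals are wide (half-width 0.47 SD at n = 20). And if levels are truly normal, the fixed log scale loses power at n = 40: 69.2 − 67.8 = 1.4 points at CV 0.2, and 69.4 − 64.9 = 4.5 at CV 0.3.
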